blood, and returning the remaining blood back to the donor. Leukocytes in plasma will be collected into a blood collection bag. Upon completion of the donation, the collection bag is labelled, packaged, and transported to the CMF. In addition, a data logger will be used to obtain a continuous record of the internal temperature of the container during transportation. A medical courier service will be used to transport the container to the CMF. Full details describing the requirements for transportation of the autologous collection bags are provided in the "Transportation of Autologous Donation SOP".

An aliquot of the apheresis product will be stored in the biorepository at the Ottawa Hospital Research Institute (OHRI) for quality testing. In addition, a portion of any unused apheresis product may be stored for future research to further optimize cell manufacturing processes in order to improve the efficacy of the cell therapy product. Samples will be stored for no longer than 15 years, and no genetic testing will be performed.

5. Randomization

Eligible participants will be randomized only following the completion of a satisfactory apheresis collection and receipt of the sample by the CMF. CMF personnel who have been trained by the sponsor to perform randomizations will access the SAPPHIRE web-based randomization system available from the Ottawa Methods Centre (OMC) located at OHRI. Personnel requiring access to this system will receive individual confidential login accounts from Data Management Services at the OMC.

After accessing the SAPPHIRE randomization system, the web-page will prompt the user to confirm participant eligibility by completing an electronic randomization case report form. Once completed, the web-based program will generate a randomization number on the screen. The requesting CMF user will print the screenshot containing the randomization number and will file it in the CMF participant binder. A copy will then be scanned and emailed to the study site for placement in the participant's study file.

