Randomization to treatment allocation will be performed using a randomly permuted block design of fixed sizes of 3, stratified based on the average of the two screening 6MWD test results (\leq 300 m vs. > 300m) and type of PAH (scleroderma associated PAH vs. all other eligible PAH types). Since our sample size for this late phase trial is relatively small, stratification is used to promote balance across the arms with respect to the baseline measure of the primary outcome, as well as type of PAH, an important prognostic factor for response to therapy. In particular, scleroderma associated PAH tends to progress more rapidly and show less favourable response to PAH-specific therapies. The allocation sequence will be generated using a computer-generated algorithm operated by the unblinded statistician for the trial located at the OMC. The study sponsor/CRO will monitor all randomizations throughout the conduct of the trial. The OMC will also generate a blinded email notification to the study site, study sponsor, and the CMF as confirmation of successful randomization. The CMF will subsequently receive a notification with the unblinded treatment allocation in order to proceed with manufacturing of the participant's study product.

6. Study Product Manufacturing

The following sections will briefly describe the methods for gene and cell manufacture and the procedures for *ex vivo* gene transfer.

6.1. Human eNOS minicircle DNA manufacture:

The human eNOS gene was derived from human umbilical vein endothelial cells, and its sequence and activity was verified as previously described (see *Investigator Brochure*). It has been subcloned into the minicircle vector (System Biosciences), with the final eNOS minicircle product manufactured by Aldevron in accordance with cGMP source manufacturing procedures.

6.2. EPC isolation and culture:

The apheresis product will be enriched for monocytes by a process similar to Ficoll gradient centrifugation using the closed-system Sepax cell separation device (Biosafe SA) and cultured in a GMP compliant cell manufacturing facility located at the OHRI. The cells are cultured in media containing human serum (tested to be free of specific infectious agents) and recombinant human growth factors and cytokines. Full details of cell culture are provided in the cell manufacturing Standard Operating Procedures (SOPs) provided to Health Canada in the chemistry and manufacturing information in Module 3 of the Clinical Trial Application.

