Since there is no antidote to cell therapy, the need for emergency unblinding during the 12 month treatment/follow-up period will be unlikely; however, unblinding may be undertaken if it is thought to be essential for effective treatment and management decisions for the study participant. The site Investigator will be responsible for contacting the trial medical consultant, [name], directly to discuss the rationale for unblinding. After consultation with [name] (or delegate), if there is a need to unblind, [name] will then contact the Manager of Data Management Services at the Ottawa Methods Centre (OMC) to ascertain the actual treatment assignment. The OMC is available 24 hours/day, 7 days/week. [name] will then relay the treatment assignment to the site Investigator. The participant will then no longer receive any further planned administrations of study product but will be followed for the duration of their study period as an "off-protocol" study participant. Study personnel will record and report the unblinding as a protocol violation. Protocol violations related to unblinding will be monitored by the Study Executive and DSMB. Local personnel in the cell manufacturing facility (CMF) will also have a record of the participant's treatment allocation.

9.2. Treatment Blinding:

Treatment allocation will remain blinded to all study participants, investigators, clinical research staff, persons performing study assessments/procedures, and data analysts from the time of randomization until database lock. Only the following study personnel will have access to unblinded treatment allocation: the unblinded study statistician and CMF personnel responsible for study product manufacturing. The study statistician will be the author of the Master Randomization List and will act as the primary contact to the CMF for any questions pertaining to study treatment allocation. The total processing period in the CMF will be equal (7±2 days) for all study products, including placebo, in order to maintain blinding of the investigator and clinical research staff. The OMC study statistician will securely maintain the confidentiality of the Master Randomization List from all other parties involved in the trial prior to database lock.

9.3. Study Stopping Criteria:

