Treatment allocation will remain blinded to all study participants, investigators, clinical research staff, persons performing study assessments/procedures, and data analysts from the time of randomization until database lock. Only the following study personnel will have access to unblinded treatment allocation: the unblinded study statistician and CMF personnel responsible for study product manufacturing. The study statistician will be the author of the Master Randomization List and will act as the primary contact to the CMF for any questions pertaining to study treatment allocation. The total processing period in the CMF will be equal ( $7\pm2$  days) for all study products, including placebo, in order to maintain blinding of the investigator and clinical research staff. The OMC study statistician will securely maintain the confidentiality of the Master Randomization List from all other parties involved in the trial prior to database lock.

Emergency Unblinding

Since there is no antidote to cell therapy, the need for emergency unblinding during the 12 month treatment/follow-up period will be unlikely; however, unblinding may be undertaken if it is thought to be essential for effective treatment and management decisions for the study participant. The site Investigator will be responsible for contacting the trial medical consultant, [name], directly to discuss the rationale for unblinding. After consultation with [name] (or delegate), if there is a need to unblind, [name] will then contact the Manager of Data Management Services at the Ottawa Methods Centre (OMC) to ascertain the actual treatment assignment. The OMC is available 24 hours/day, 7 days/week. [name] will then relay the treatment assignment to the site Investigator. The participant will then no longer receive any further planned administrations of study product but will be followed for the duration of their study period as an “off-protocol” study participant. Study personnel will record and report the unblinding as a protocol violation. Protocol violations related to unblinding will be monitored by the Study Executive and DSMB. Local personnel in the cell manufacturing facility (CMF) will also have a record of the participant’s treatment allocation.

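### Does having cell manufacturing facility staff request randomisation break allocation concealment?

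*Protocol*

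**What the plan says.** Protocol 5, repeated in SAP 2.2, gives the request to the CMF: "CMF personnel who have been trained by the sponsor to perform randomizations will access the SAPPHIRE web-based randomization system". At that point "the web-page will prompt the user to confirm participant eligibility by completing an electronic randomization case report form". The timing is fixed: "Eligible participants will be randomized only following the completion of a satisfactory apheresis collection and receipt of the sample by the CMF". The list is a "randomly permuted block design of fixed sizes of 3", stratified by screening 6MWD and by type of PAH.

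Two notices follow. First, "The OMC will also generate a blinded email notification to the study site, study sponsor, and the CMF". Then, "The CMF will subsequently receive a notification with the unblinded treatment allocation", so that the product can be made. Protocol 9.1 adds, on emergency unblinding: "Local personnel in the cell manufacturing facility (CMF) will also have a record of the" allocation.

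The access rule is in Protocol 9.2 and, in the same words, SAP 2.2 (Blinding): "Only the following study personnel will have access to unblinded treatment allocation: the unblinded study statistician and CMF personnel responsible for study product manufacturing".

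**The concern.** The unit that asks for the next assignment is also the unit that holds all the previous ones, and neither document says that different people do the two jobs. Small fixed blocks whose size is printed in the protocol make past allocations informative about the next one.

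If one person did both jobs, the form completed at the CMF would be a place where someone who could foresee the arm might hold back or delay an eligible participant, or call a collection inadequate. That would weaken allocation concealment in a trial of 45 participants. It would leave the type I error rate, power and sample size as they are, and it would not in itself show bias in 6MWD.

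**Working it through.** **Inputs.** 45 randomised (Protocol 11.1); 2 x 2 = 4 strata and blocks of 3 with one place per arm (Protocol 5); Arms 2 and 3 active in Course 1 (Protocol 3). The stratum shares are not given, so they are assumed and varied.

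**The plan's own figure.** The documents give no figure for predictability. The sample size reproduces: residual SD = 85 x sqrt(1 - 0.80^2) = 51.0 m; standard error with 13 against 26 = 51.0 x sqrt(1/13 + 1/26) = 17.3 m; 50/17.3 = 2.89; noncentral t with 35 df gives 80.1% power, against 80% stated. None of these inputs depends on who makes the request.

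**Step 1: one complete block, earlier places known.** The third place is always certain, so the exact arm is known for 1 place in 3. Course 1 status is known at the third place, and at the second if the first was placebo (chance 1/3). That is 1 + 1/3 = 4/3 places per block, or 4/9 = 44.4%.

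**Step 2: 45 participants in four strata.** Each stratum ends with 0, 1 or 2 participants in an open block, about 1 on average.

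- Complete blocks: about (45 - 4)/3 = 13.67, so the exact arm is certain for about 13.7 (30%).
- Status certain: (4/3) x 13.67 + 4 x (1/3) x (1/3) = 18.22 + 0.44 = 18.67 (41%). The second term covers open blocks holding two participants.

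The exact binomial calculation gives 13.66-13.70 and 18.66-18.69. It covers 25 settings with assumed scleroderma shares of 10-50% and assumed shares with 6MWD of 300 m or less of 30-70%.

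**Step 3: how much of this is new information.** Placebo is certain only when it falls in the third place: 13.67/3 = 4.6 participants. The other 18.7 - 4.6 = 14.1 are certain active, which the 2:1 ratio already makes the better guess. Correct best guesses: 13.67 + (2/3) x 31.33 = 34.56, and 34.56/45 = 76.8%. Guessing active every time gives 30/45 = 66.7%. The gain is about 4.6 correct guesses in the whole trial.

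**Step 4: what the requester must know.**

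| Requester knows | Status certain, of 45 | Exact arm certain | Best guess of status |
|---|---|---|---|
| Earlier allocations and the new stratum | 18.7 (41%) | 13.7 (30%) | 76.8% |
| Earlier allocations, not the new stratum | 0.3-0.5 (about 1%) | about 0.01-0.02 | 69-73% |
| No allocations | 0 | 0 | 66.7% |

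The middle row comes from simulation (1,500 runs at each of 9 settings). The first row needs a requester who also manufactures, tracks allocations by stratum and knows the new stratum. No passage says that the requester manufactures. That the stratum is entered at the CMF is an inference: a CMF user completes the form, and SAP 3.2 foresees stratification errors at randomisation.

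**Step 5: what could be done with the knowledge.** With fixed lists, a delay changes a participant's arm only if someone else in the same stratum is randomised meanwhile. Assume even accrual of 45 over the 5 years in SAP 2.1, or 9 a year, and stratum shares of 10-55%.

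- Over 11 days (the usual maximum from apheresis to dosing, Protocol 7.1): 9 x 11/365 = 0.271 randomisations expected. The chance is 1 - exp(-0.0271) = 3% to 1 - exp(-0.149) = 14%.
- Over 90 days: 2.22 expected, giving 20% to 70%. So long a hold would mean a rejected collection and a repeat apheresis, which the site would see.

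**Step 6: the passages side by side.** The access rule is exclusive, so a CMF user who randomises but does not manufacture is already barred from allocations. A blinded notice to the CMF ahead of the unblinded one makes most sense if some CMF users stay blinded. Logins are individual and confidential (Protocol 5). Sites screen, obtain consent and perform apheresis before any request (Protocol 4.3 and 4.4), and Appendix F gives the site's Principal Investigator overall responsibility for the collection. Outcome assessors and analysts are blinded (Protocol 9.2).

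**The case for a change.** The strongest contrary case is that implication is not a rule. The access restriction does not forbid manufacturing staff from also being trained to randomise, and Protocol 9.1 speaks more broadly of local CMF personnel. Neither document says who judges a collection acceptable. The monitoring in Protocol 5 covers randomisations made, and as worded does not reach a participant who is delayed or never randomised. SAP 3.2 places source verification of eligibility after randomisation, so the CMF form is the last described eligibility check before allocation. One sentence would put the matter beyond doubt at almost no cost.

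The factual part stands: no sentence separates the two roles. The inference that the plan would therefore go wrong does not. It needs a dual-role requester whom the documents never describe, acting on participants whom a blinded site has already found eligible and put through apheresis. The site would notice if one were dropped. Staffing of this kind is ordinarily set in a facility's procedures and training records, which were not available.

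The companion remedies add little. A log of sample acceptance has nothing further to protect once the requester cannot see allocations. Random blocks of 3 and 6 without role separation would still leave 4.7-5.0 statuses certain, and would raise the SD of the Arm 1 count from about 0.77 to about 0.91-0.95.

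**Conclusion.** No change to the plan is needed. The documents leave a detail of role assignment unstated, and the existing access rule and the two-stage notification already point to the sensible way of filling it: a CMF user outside manufacturing makes the request. Following the plan as written would not produce a wrong result.

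The 41% (status) and 30% (exact arm) figures are upper bounds. They require knowledge of every earlier allocation and of the new participant's stratum. Without the stratum about 1% of statuses are certain, and without allocations none are. Even at the bound, the gain is about 4.6 correct guesses among 45.

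The conclusion rests on reading the access rule as exclusive, and on blinded sites controlling screening, apheresis and outcome assessment, as the documents say. It would need another look if CMF records showed the same person both requesting randomisation and receiving allocations. Nothing in the documents shows that.

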The primary endpoint is the 6 minute walk distance (6MWD) at 6 months. The primary effect measure is difference in 6MWD at 6 months between patients receiving a course of 4 monthly doses of eNOS-EPCs compared to placebo. As well, a number of secondary endpoint measures will be performed to provide additional insights into the safety and efficacy of this treatment.

Study participants will be randomized into one of three arms (**Figure 1**):

- **Arm 1**. Four monthly IV injections of the placebo saline solution (Plasma-Lyte A) in the first 6 months (Course 1) followed by four monthly IV injections of 20 million autologous eNOS-transfected EPCs in the second 6 months (Course 2; total cumulative dose of 80 million cells).
- **Arm 2**. Four monthly IV injections of 20 million autologous eNOS-transfected EPCs in the first 6 months (Course 1) followed by four monthly IV injections of placebo (Plasma-Lyte A) in the second 6 months (Course 2; total cumulative dose of 80 million cells).
- **Arm 3**. Four monthly IV injections of 20 million autologous eNOS-transfected EPCs in the first 6 months (Course 1) followed by a repeat of four monthly IV injections of 20 million eNOS-

transfected autologous EPCs in the second 6 months (Course 2; total cumulative dose of 160 million cells).

[figure not shown]

Figure 1: The SAPPHIRE 3-Arm trial design.

Rationale for the 3-arm trial design: The SAPPHIRE trial is designed to maximize the generation of relevant results to inform further development or application of the cell therapy approach. The rationale for the main elements of the study is summarized below.

- **Course 1:** The first 6 months of the study has a standard design with 2:1 randomization to study product or placebo:
 - o Arm 1: Participants will receive 4 monthly placebo injections.
 - o Arms 2 and 3: Participants will receive 4 monthly injections of the cell therapy product.

The primary effect measure is at the 6 month time point.

However, the study continues beyond 6 months in order to address a number of important secondary endpoints. *Importantly, the blind will continue over the entire 12 month period of the study*.

• Course 2: In the second 6 month period, the study treatments will be altered to address specific questions about the timing and durability of this cell therapy:

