- Withdraw from study follow-up procedures and assessments and decline further contact and access to personal health information and indicate data collected to date cannot be used

in the final analysis. Source documents cannot be destroyed until completion of the long-term storage period (25 years).

The primary reason for premature withdrawal and the participant's decision to decline study follow-up must be recorded in the participant's source documents and on the Treatment Phase Exit eCRF.

9.6. Lost To Follow-up:

In the case of a participant becoming lost to follow up, the investigator should demonstrate "due diligence" by performing the following recommended steps:

- Contact participant three times and clearly document those efforts. Contacts may be done either by telephone contacts, email or mail correspondence. Documentation of any telephone contacts should also include dates and times
- If unsuccessful after three times, a registered letter should be sent to the participant's address requesting the participant to sign for the letter to attempt to confirm survival status
- If no response, clearly document efforts and complete all source documents and eCRFs as applicable
- Confirm status as lost to follow-up.

9.7. Pregnancy:

In the event that a participant becomes pregnant during the 12-month treatment phase of the trial, the following steps should be taken:

- The participant will not receive any further study product injections
- The site Investigator will contact the study medical consultant, [name] (or delegate), within 24 hours of their knowledge of the pregnancy to request unblinding of the participant's treatment allocation
- If the unblinding reveals that the participant has received at least one cell dose, she will continue to be followed for the duration of her pregnancy and the treatment phase according the protocol visit schedule and procedures, with the exception of imaging tests and right heart catheterizations. In addition, the long-term follow-up registry annual calls should be completed.
- Following birth of the baby, health information at birth should be collected and filed with source documents and entered in the Pregnancy Follow-up eCRF. In the event of any medical concerns at birth, an adverse event form or serious adverse event form should be completed as appropriate

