- If the unblinding reveals that the participant has not received at least one cell dose, the participant will be withdrawn from the trial with a study exit visit completed (section 9.8).

9.8. Treatment Phase Premature Withdrawal Visit:

In the event of early withdrawal from the 12-month treatment phase of the trial, a Premature Withdrawal visit will be completed with the following timing:

- 1. 30 ± 2 days after the last study product injection (for participants who exit the treatment phase between Months 0-4 or 6-10)
- 2. 5 ± 2 days following withdrawal from the treatment phase (for participants who exit the treatment phase between Months 4-6 or 10-12)

The following assessments will be performed:

- Physical exam by the principal investigator or co-investigator
- Concomitant medication recording
- Vital signs (blood pressure, heart rate, respirations)
- Assessment and recording of WHO functional class (see Appendix C)
- O₂ saturation (peripheral device)
- Laboratory tests: sodium, potassium, chloride, TCO₂, blood sugar, BUN, creatinine, calcium, magnesium, phosphorus, alkaline phosphatase, total bilirubin, CPK, troponin, AST (SGOT), ALT (SGPT), LDH, gamma GT, albumin, uric acid, serum ferritin, CBC with differential, ESR, PT, PTT, INR, brain natriuretic peptide (BNP), C-reactive protein (CRP)
- Urine collection for routine and microscopic analysis
- Urine pregnancy test for females with childbearing potential
- 6MWD test and Borg dyspnea index (see Appendix D and E)
- Resting 12 lead ECG
- Assessment of adverse events and serious adverse events

10. Adverse Event Reporting

10.1. Adverse Event (AE):

An adverse event is any untoward medical occurrence in a research participant administered an investigational product and which does not necessarily have a causal relationship with the study product. An AE can therefore be any unfavourable and unintended sign (including an abnormal lab finding, for example), symptom, or disease temporally associated with the use of an investigational product, whether or not considered related to the investigational product.

The following definitions are to be used for guidance for determining severity of adverse events:

- Mild An awareness of symptoms but easily tolerated
- Moderate Symptoms interfere with normal daily activities
- Severe Symptoms are incapacitating with inability to perform daily activities

10.2. Adverse Drug Reaction (ADR):

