## 3.3 Analysis populations

The primary analyses will be by intent-to-treat but we will also conduct "per protocol" and "as treated" analyses.

Intent-to-treat analysis will include all randomized participants, including those who have not received a dose of the study product. Analysis will be based on the initial treatment assignment.

Per protocol analysis will include all randomized participants who have received at least 3 doses of the allocated study product during the first course of treatment (first 6 months), and at least 3 doses of the allocated study product during the second course of treatment (second 6 months), with all primary outcome measures having been captured.

As treated analysis will include all randomized participants who have received at least 1 dose of the study product. Analysis will be based on the actual treatment received rather than on the initial treatment assignment.

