## 4.2 Withdrawal/Follow-up

### Premature Participant Withdrawal

Premature withdrawal of study participants may be based on any of the following reasons:

- Sponsor Recommendations (i.e. Safety-specific protocol requirements)
- Investigator Decision (i.e. Participant non-compliance or if participant cannot safely perform the procedures required in the protocol)
- Participant Decision (No longer wishes to take part in the trial)
- Death of the study participant
- Pregnancy during the 12 month study treatment/follow-up period (refer to Section 9.7 for guidance)

Following the receipt of the study product, a participant may withdraw consent for study follow-up at any time for any reason. In addition, a participant may be considered withdrawn for failure to return for study visits or become lost to follow up for any other reason.

If a participant withdraws consent for further study follow-up procedures and assessments, every effort should be made to continue to follow the participant for their safety and the collection of safety data. This would ideally include completion of a treatment phase premature withdrawal visit (see Treatment Phase Premature Withdrawal Visit) and the long-term follow-up registry annual phone calls.

The PI or research staff must determine whether the participant wishes to:

- Withdraw from study follow-up procedures and assessments, but permit telephone follow-up or review of clinic/hospital records for data collection
- Withdraw from study follow-up procedures and assessments and decline further contact, however permit their accumulated data to be included in the study analysis
- Withdraw from study follow-up procedures and assessments and decline further contact and access to personal health information and indicate data collected to date cannot be used in the final analysis. Source documents cannot be destroyed until completion of the long-term storage period (25 years).

The primary reason for premature withdrawal and the participant's decision to decline study follow-up must be recorded in the participant's source documents and on the Treatment Phase Exit eCRF.

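### After a pregnancy, collection of the Month 6 walk depends on the unblinded treatment: among dosed participants before Month 6 it is stopped in Arm 1 and continued in Arms 2 and 3

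*Protocol*

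**What the plan says.** Protocol 9.7 stops injections once a participant is pregnant and has the investigator contact the medical consultant "within 24 hours of their knowledge of the pregnancy to request unblinding". Two branches follow.

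- **At least one cell dose received:** "she will continue to be followed for the duration of her pregnancy and the treatment phase according the protocol visit schedule and procedures". Only imaging and catheterization are excused. The 6MWD is not among the exceptions, so it remains due. The annual registry calls are also kept.
- **No cell dose received:** "If the unblinding reveals that the participant has not received at least one cell dose, the participant will be withdrawn from the trial", with the exit visit of Protocol 9.8.

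Protocol section 3 fixes who has had cells before the primary endpoint. For Course 1 it states "Arm 1: Participants will receive 4 monthly placebo injections" and "Arms 2 and 3: Participants will receive 4 monthly injections of the cell therapy product". Arm 1 first receives cells at the Month 6 visit, and Appendix H makes product delivery the last procedure of a visit, so the Month 6 walk comes first.

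Protocol 9.1, repeated in SAP 2.2, treats emergency unblinding differently. Study product stops, but the participant is followed for the rest of the study period, with no condition on what she received.

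SAP 4.2 lists among the reasons for withdrawal "Pregnancy during the 12 month study treatment/follow-up period (refer to Section 9.7 for guidance"). That section is in the protocol. The SAP neither reproduces it nor says how these withdrawals are handled. SAP 3.3 defines the primary population: "Intent-to-treat analysis will include all randomized participants, including those who have not received a dose of the study product".

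**The concern.** Ordinary withdrawal can happen in any arm for reasons unrelated to the code. Here the rule itself reads the code. Among women who have been dosed and become pregnant before Month 6, having had no cell dose is the same as being in Arm 1. The primary contrast compares Arms 2 and 3 with Arm 1 at Month 6, so for the same event the protocol stops collecting the outcome on one side and continues on the other. The losses fall on the smaller group, 15 against 30.

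Two further comparisons are touched. The 6-month death or clinical worsening endpoint is compared by chi-square and relative risk (Protocol 11.8), with no stated rule for participants withdrawn before Month 6. In Course 1, retention or withdrawal after a pregnancy also reveals treatment to anyone who knows the rule. A retained woman continues to have her walk and WHO class assessed, and both feed the clinical worsening definition.

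**Working it through.** **1. Who is affected.**

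| Situation when the pregnancy is known | Cell dose received? | Follow-up under 9.7 |
|---|---|---|
| Arm 1, dosed, before Month 6 | No | Exit visit, then withdrawn |
| Arm 2 or 3, dosed with cells, before Month 6 | Yes | Visits continue; Month 6 walk due |
| Arm 2 or 3, before any cell dose | No | Exit visit, then withdrawn |
| Arm 1, after a Course 2 cell dose | Yes | Visits continue |

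The asymmetry is therefore mainly a Course 1 matter. Catheterization and imaging are dropped for retained women too, so Month 6 PVR and RV imaging are not collected after a pregnancy in any arm.

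**2. Whether the exit walk replaces Month 6.** Protocol 9.8 includes a 6MWD. For exits in Months 0-4 it takes place 30 ± 2 days after the last injection. The last Course 1 injection is at Month 3, so this walk falls at about Month 4 at the latest. For exits in Months 4-6 it takes place 5 ± 2 days after withdrawal, that is 3 to 7 days. The Month 6 window is ±5 days, so the exit walk lands in it only if withdrawal occurs between 5 + 7 = 12 days before and 5 − 3 = 2 days after Month 6. It generally does not replace the Month 6 walk.

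**3. The plan's power figure.** Inputs from Protocol 11.1: SD 85 m, correlation 0.80, difference 50 m, two-sided 5%, 13 per arm (13 against 26).

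- Residual SD = 85 × √(1 − 0.80²) = 51 m.
- Noncentrality = 50 / (51 × √(1/13 + 1/26)) = 2.89, with 39 − 4 = 35 degrees of freedom (three arms and one covariate).
- Power by noncentral t = 80.1%. The stated 80% reproduces.

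**4. Cost of lost placebo walks**, by the same formula:

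| Placebo walks lost | From 15 vs 30 | From 13 vs 26 |
|---|---|---|
| 0 | 85.7% | 80.1% |
| 1 | 84.0% | 77.9% |
| 2 | 82.1% | 75.4% |
| 3 | 79.9% | 72.4% |

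The first column assumes no other attrition. The second assumes the planned attrition has already happened.

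**5. Share of the placebo outcome.** One loss is 1/15 = 6.7% of Arm 1, against 0/30 in Arms 2 and 3 for the same event after a cell dose.

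**6. Expected number.** No rate is given. Assume 0 to 2 pregnancies before Month 6, equally likely for each participant. Arm 1 holds 15/45 = 1/3 of participants, so the expected placebo losses are 0 to 2 × 1/3 = 0.67, or at most 0.67/15 = 4.4% of Arm 1.

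**7. Possible shift.** In a simple comparison of observed means, if *k* lost women would have differed by *b* metres from the rest of Arm 1, the observed placebo mean is off by −*k*·*b*/15. With an assumed *b* of ±50 m the size is 50/15 = 3.3 m for one loss and 100/15 = 6.7 m for two, against a target of 50 m. Earlier walks in the repeated-measures model would reduce this.

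**The case against.** A reader might infer that 9.7 contradicts the intent-to-treat definition. It does not. SAP 3.3 defines that population by who is included and how they are classified; it does not require complete follow-up. A withdrawn Arm 1 participant stays in the set and in Arm 1, and her earlier walks stay in the model.

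A reader might also infer that arm-dependent missingness biases the primary estimate. That does not follow. Arm enters through the group-by-time terms, so unequal missingness alone does not bias a likelihood analysis. Bias also requires the uncollected walks to differ from what arm and earlier walks predict. The documents do not show this either way. A missing-not-at-random imputation is already planned (Protocol 11.10), although it is general and does not address losses that the protocol creates by allocation.

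A third tempting reading is that 9.7 breaches the blinding rule in 9.2. Sections 9.1 and 9.7 are express exceptions to it, and nothing says that the allocation goes to the staff who run the walk.

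Finally, abstinence or two contraceptive methods are required, the sample size allows 10% attrition, and following cell-exposed pregnancies has an evident safety purpose. All of this stands and keeps the point small. It does not explain why a placebo participant's outcome visits should end when 9.1 would continue them.

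**Conclusion.** The point holds as a minor design asymmetry of low probability. After a pregnancy before Month 6, whether a dosed participant's primary outcome is collected is decided by her unblinded treatment. Sections 9.7 and 9.1 differ on outcome follow-up after unblinding. This is a stated rule, not a missing detail.

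The cost is 6.7% of Arm 1's Month 6 walks per affected participant and roughly 2 to 3 points of power for each of the first three losses. If there is no other attrition, one or two losses leave power above 80%; if the planned attrition has already occurred, power falls below it. These figures rest on the protocol's SD and correlation, on a simple covariance analysis in place of the full repeated-measures model, and on an assumed number of pregnancies. The documents do not support calling this a demonstrated bias, and its direction is unknown. The loss is also not strictly confined to the placebo arm, since a participant in Arm 2 or 3 found pregnant before any cell dose is withdrawn too.

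**What to change.** Reconcile 9.7 with 9.1 so that outcome collection after a pregnancy does not depend on allocation. The simplest form gives every pregnant participant the non-imaging, non-invasive assessments that 9.7 already keeps for cell-treated women, including the 6MWD where the investigator judges it feasible. State that the disclosed allocation is kept, where possible, from staff who run the walk or rate WHO class. Add a sentence to SAP 4.2 on how data after a pregnancy enter the 6-month analyses, so that it no longer relies on a bare cross-reference.

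The rules on study product and on clinical care in pregnancy are left to the sponsor and are not part of this change. The cost is a one-paragraph protocol amendment, matching SAP text, and a few extra routine visits for very few participants.
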